7.3 Claims and intended performance

In this clinical investigation the following promotional claims shall be supported:

Table 1: List of promotional claims related device features and study endpoint

Promotional Claim	Feature	Related endpoints / data of interest
- suited for any anatomy (even muscular, thin etc.)	BIOMONITOR III: Miniaturization, maintaining original rigid-flex design	Assessment of insertion procedure
- industry-leading high R-wave sensing (as prerequisite for reliable arrhythmia detection)	BIOMONITOR III: ~70 mm sensing vector	R-wave amplitude
- improved visual arrhythmia assessment due to P-wave visibility - x% P-wave visibility	BIOMONITOR III: - Lossless sECG-compression - long sensing vector - fractal coating - low HP-filter	Assessment of P-wave visibility

Promotional Claim	Feature	Related endpoints / data of interest
- fast subcutaneous injection-like procedure	Incision/Insertion Tool: complete tool-set with implant premounted	Assessment of insertion procedure
- highly reliable remote monitoring guarantees daily availability of important information through Home Monitoring - TSI of > 90%	BIOMONITOR III / HM: Daily Transmission	Home Monitoring transmission success
- Patient-individualized, indication-based, quick and accurate programming - rare need for re-programming/adaptation	BIOMONITOR III: Indication-based Program-Sets	Assessment of device programming
- Clinical rather than technical programming	BIOMONITOR III: Software User Interface	Assessment of device programming
- Highly sensitive syncope-diagnosis as the device is robust against oversensing - Highly specific syncope-diagnosis as the device is robust against undersensing, thus low review burden - State-of-the-art asystole detection (sensitivity, specificity, positive-predictive-value and negative-predictive-value) in combination with superior R-wave sensing	BIOMONITOR III: Asystole detection	Supportive episode data collection (Home Monitoring)
- Highly sensitive and the same time highly specific AF-diagnosis as the device is robust against over- and undersensing - High AF-specificity, thus low review burden - State-of-the-art AF-detection (sensitivity, specificity, positive-predictive-value and negative-predictive-value) in combination with superior R-wave sensing	BIOMONITOR III: AF detection	Supportive episode data collection (Home Monitoring)
- Highly sensitive and specific arrhythmia diagnosis as the device is robust against over- and undersensing - low review burden - State-of-the-art arrhythmia-detection (sensitivity, specificity, positive-predictive-value and negative-predictive-value) in combination with superior R-wave sensing	BIOMONITOR III: Brady-, HVR-, SRD-detection algorithms	Supportive episode data collection (Home Monitoring)

FOR-137-014-F / SOP-137-020.020 / CRQI70002722

Promotional Claim	Feature	Related endpoints / data of interest
- reliable trigger functionality/ high successful trigger rate	Remote Assistant III: Patient-triggered episode- recording	Remote Assistant trigger success rate

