sECG	Subcutaneous Electrocardiogram
SOP	Standard Operating Procedure
SW	Software
TGA	Therapeutic Goods Administration
T-LOC	Transient Loss of Consciousness
TSI	Transmission Success Index
UBD	Used before date
UMTS	Universal Mobile Telecommunications System
USA	United States of America
USADE	Unanticipated Serious Adverse Device Effect
USB	Universal Serial Bus
VER	Validation Report
VES	Ventricular extrasystole
VIC	Victoria
Vs	Number of Ventricular Sensing Events

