2 SYNOPSIS

Title	BIO CONCEPT.BIOMONITOR III
Patient population	The patient population consists of patients in whom long-term cardiac rhythm monitoring may be required for diagnostic purposes.
Design	Open, prospective, single arm, non-randomized design
Investigational device(s)	
 • BIOMONITOR III implantable cardiac monitor, including incision and insertion tools • Remote Assistant III • Programmer Software (PSW 1901.A/S)
Objectives	The objective of this study is to assess the insertion procedure, use and handling of the incision / insertion tools and to assess the sensing quality of the BIOMONITOR III implantable cardiac monitor.
Primary / secondary endpoints	None
Data of interest	
 • Assessment of insertion procedure • Assessment of use and handling of insertion and incision tools • Assessment of R-wave amplitude • Collection of subcutaneous ECGs (sECGs) based on Home Monitoring over one month • Noise burden • Adverse events • Adverse device effects (procedure / device related) • Evaluation of P-wave visibility based on collected sECGs • Home Monitoring transmission success • Remote Assistant III trigger success
Inclusion criteria	
 • Patient is at high risk of developing a clinically important cardiac arrhythmia; or 
Patient is undergoing investigation for symptoms such as palpitations, pre-syncope or syncope, that are suggestive of an underlying

cardiac arrhythmia; **or**

Patient is undergoing investigation for the detection of atrial fibrillation following cryptogenic stroke; **or**

Patient is planned for AF ablative procedure or has already undergone an AF ablative procedure.

- Patient is able to understand the nature of study and has provided written informed consent.
- Patient is willing and able to perform all follow up visits at the study site.
- Patient is willing and able to use the CardioMessenger and accepts the BIOTRONIK Home Monitoring concept.

Exclusion criteria

- Patients implanted with ICD or pacemaker.
- Patient is pregnant or breast feeding.
- Patient is participating in another interventional clinical investigation.
- Patient is less than 18 years old.
- Patient's life-expectancy is less than 6 months.

Study duration

~ March 2019 – June 2019 (approx. 4 months)

Sample size

up to 45 patients

Follow-up scheme

- Patient enrollment / baseline assessment with insertion procedure and pre-hospital discharge

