4.7.1.11 Home Monitoring, ReportShare and BIOTRONIK Patient APP

The BIOTRONIK cardiac monitors provide a complete diagnosis management system:

With **Home Monitoring**, diagnostic information as well as device technical data are automatically and wirelessly sent to a stationary or mobile transmitter (CardioMessenger Smart) via an antenna in the lead body. The data are encrypted and sent from the transmitter to the BIOTRONIK Home Monitoring Service Center (HMSC) through a cellular phone network.

ReportShare is software that allows the physician to upload follow-up interrogated during an in-office follow-up to the HMSC by using a UMTS-capable Renamic programmer and a cellular phone network connection. The received data are deciphered and evaluated. Each physician can set the criteria for evaluation to be used for each patient and can configure the time of notification within the HMSC.

A clear overview of the results of this analysis is displayed for the attending physicians on the protected Internet platform (Home Monitoring Service Center) and can be exported in a PDF-format (‘ CardioReport ’).

Data transmission from the device is performed with a daily device message. Device messages that indicate special events in the heart or in the device are forwarded at the pre-set time. A test message can be initiated at any time using the programmer to immediately check the Home Monitoring function.

Important medical information includes the following:

- Sustained atrial arrhythmias
- Sustained ventricular arrhythmias
- Current statistics

- Periodically recorded subcutaneous ECGs that are transmitted according to an individually adjustable timing interval in addition to the regular device message

For documentation of medical symptoms, the patient has the option to download the BIOTRONIK **Patient APP** for use with a private smartphone. The Patient APP software provides a symptoms diary in which the patient may describe the exact time of occurrence, nature and duration of medical symptoms (see Figure 7). Data of the symptom diary will be transmitted via cellular networks to BIOTRONIK and will be made available to the investigator via the BIOTRONIK Home Monitoring Service (see above). The symptom diary may therefore ease the workflow for the investigator. However, the Patient APP software **is no emergency system**. In the event of an emergency or disturbances, the patient is asked to seek medical care and go to available medical facilities.

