7.2.2 Data of interest

Information will be collected to characterize the insertion of the BIOMONITOR III and the safety and efficacy of the BIOMONITOR III system. The data will be statistically analyzed, where appropriate (see section 11). Specifically, the following data of interest will be analyzed:

- Insertion success rate
- R-wave amplitude measured at insertion and at 1 week / 1 month after insertion.
- Noise burden at 1-week follow-up and 1-month Home Monitoring observation
- Adverse events and device deficiencies associated with insertion procedure and insertion tools
- Remote Assistant trigger success rate
- Home Monitoring transmission success rate

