8.3.6 Timelines

First patient in (FPI): ~ Feb 2019

Last patient in (LPI): ~ May 2019

Enrollment period: ~ 3 months

Last patient out (LPO): ~ Jun 2019

Duration of study participation: ~ 1 month

Finalization of study report ~ Sep 2019

The end of the clinical study is defined as the date of termination of the last patient (last patient out).

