18.7 Anticipated adverse events

The following peri- or post-operative risks are anticipated with the insertion of the BIOMONITOR III and are therefore assessed as procedure related adverse device effects. They are listed in **Table 3** as sorted by their incidence rates. For all references used for this chapter, refer to the list at the end of this section.

Table 3: Anticipated AEs based on literature research sorted by incidence rate

Frequency	Event Type	Reference ID
Frequent 1 to 10 patients out of 100	Insertion site irritation/soreness	4, 9
	Insertion site erosion	3, 9
	Insertion site pain	1, 2, 3, 5, 8, 11
	Insertion site dehiscence/device protrusion/extrusion	2, 7, 13, 15
	Insertion site infection	1, 2, 3, 5, 6, 7, 8, 9, 10, 11, 12, 15
	Insertion site hematoma	3, 7, 14
Occasionally 1 to 10 patients out of 1.000	Insertion site hemorrhage	1, 8, 13
	Insertion site discomfort	5, 12
	Insertion site bruising	2, 13
	Incision site complication	8, 13
	Device dislodgement/migration	3, 5, 13, 14
Not known Frequency not assessable on the basis of the available data	Oversensing, Undersensing, Premature battery depletion, Electromagnetic interference (EMI), Impaired healing, Insertion site rash, Non-insertion site rash, Non-insertion site pain, Numbness of upper arm, Procedural dizziness, Post procedural dizziness, Post procedural nausea, post procedural headache, Dyspnea, Vagal reaction, Presyncope, Supraventricular tachycardia, Shock/dyspnea (reaction to antibiotic administration prior to device insertion), Device interrogation issue, Home Monitoring transmission incomplete/missing, Housing surface conspicuous before implantation, Varying P/R values, Device in safety back-up mode, Silicone coating damaged, Foreign body rejection phenomena, Accumulation of fluid in the device pocket	1, 2, 3, 5, 6, 13, 16, 17

1. BIOTRONIK. CIR Master Study of the Implantable Cardiac Monitor BioMonitor 2015.
2. BIOTRONIK. CIR BioMonitor 2 Pilot Study 2016.
3. BIOTRONIK. CIR BIO|MASTER.BioMonitor 2 2017.
4. Bisignani G, Bonis S de, Bisignani A, Mancuso L, Giacomelli D. Sensing performance, safety, and patient acceptability of long-dipole cardiac monitor: An innovative axillary insertion. *Pacing Clin Electrophysiol* 2018;**41**:277–283.

FOR-137-014-F / SOP-137-020.020 / CRQ170002722

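### A Transmission Success Index above 90% can support a claim about average transmission success, but not the claim of guaranteed daily availability that Table 1 attaches to it

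*Protocol*

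**What the plan says.** Section 7.3 introduces Table 1 with "In this clinical investigation the following promotional claims shall be supported". One entry in the claim column is "highly reliable remote monitoring guarantees daily availability of important information through Home Monitoring - TSI of > 90" per cent. The feature named beside it is daily transmission, and the related data item is Home Monitoring transmission success. It is the only entry in the claim column with a numeric performance level filled in; the P-wave visibility entry still carries a placeholder percentage.

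The other places that bear on it are:

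- Section 7.2.2 lists a single item, "Home Monitoring transmission success rate". It names no per-patient completeness measure and no gap length.
- The list of abbreviations expands TSI as "Transmission Success Index". The protocol gives no numerator, denominator or level of aggregation.
- Section 4.7.1.11 sets the schedule: "Data transmission from the device is performed with a daily device message".
- Table 3 in section 18.7 includes "Home Monitoring transmission incomplete/missing" among anticipated events whose frequency is not known.
- Sections 7.2, 8.1.3 and 11.5 state that there are no hypotheses, no statistical endpoints and no pass/fail criteria.

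**The concern.** The claim and its measure concern different things. A guarantee of daily availability is a statement about every patient on every day. A transmission success index is an average, and the level attached to it allows almost one message in ten to be missing. The index can therefore reach its stated level while the claim is plainly untrue for many patients, and an average does not show which patients those are or how long their gaps last.

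This matters because section 7.3 fixes what the study is meant to support in public. Section 11.6 also plans an interim analysis of all available data to inform the decision on product launch. If the result comes out above 90%, the table as written invites the reader to treat the availability claim as supported.

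**Working it through.** **Inputs from the protocol.** One message per day (4.7.1.11); "up to 45 patients" (synopsis); "Duration of study participation: ~ 1 month" (8.3.6), taken as 30 days. The protocol gives no derivation for the 90% figure, so there is no calculation of its own to reproduce.

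**Assumptions, because the protocol does not give them.** The index is transmitted days divided by expected days, pooled over patients. The true daily rate p is varied. Days within a patient are first independent, then correlated.

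**Step 1, no model needed.** An index above 90% means that fewer than 10% of messages are missing, so on average fewer than 0.10 × 30 = 3 per patient. Even if the 90% applied to each patient separately, 28/30 = 93.3% would exceed it and 27/30 = 90.0% would not, so every patient could still miss 2 days. Neither version amounts to daily availability.

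**Step 2, independent days.** The index exceeds 90% when more than 1,215 of 45 × 30 = 1,350 messages arrive (exact binomial). The share of patients with at least one missed day is 1 − p^30.

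| True rate p | P(index > 90%) | Mean missed days per patient, 30(1 − p) | Patients with ≥ 1 missed day |
|---|---|---|---|
| 0.90 | 0.487 | 3.0 | 95.8% |
| 0.91 | 0.891 | 2.7 | 94.1% |
| 0.92 | 0.995 | 2.4 | 91.8% |
| 0.95 | > 0.9999 | 1.5 | 78.5% |
| 0.97 | > 0.9999 | 0.9 | 59.9% |
| 0.98 | > 0.9999 | 0.6 | 45.5% |

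The share with a missed day falls below half once p exceeds 0.5^(1/30) = 0.977. With 28 days and p = 0.95 it is 76.2%. Using 40 patients, to allow for the drop-out expected in 11.4, leaves the picture unchanged.

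**Step 3, missed days clustered within patients.** Beta-binomial model with p = 0.95, 45 patients and 30 days; P(index > 90%) is from 20,000 simulated trials. The mean number of missed days is 1.5 per patient throughout, so the mean among affected patients is 1.5 divided by the share affected.

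| Within-patient correlation | P(index > 90%) | Patients with ≥ 1 missed day | Mean missed days per affected patient |
|---|---|---|---|
| 0 | > 0.9999 | 78.5% | 1.5/0.785 = 1.9 |
| 0.05 | 1.000 | 61% | 1.5/0.606 = 2.5 |
| 0.2 | 0.997 | 37% | 1.5/0.366 = 4.1 |
| 0.4 | 0.98 | 23% | 1.5/0.227 = 6.6 |

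Clustering moves the shortfall from many patients with few missed days to fewer patients with more missed days each. The index stays above 90% in nearly every trial, and in no row is daily availability achieved.

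**The case against.** The strongest reply is that nothing in the protocol is decided by the 90%. The figure sits inside a promotional claim and may simply put a number on the word reliable. The study is exploratory, and section 11.5 sets no pass/fail criteria. That stands. A reader might infer a decision rule that declares the claim proven once 90% is passed; the documents contain no such rule. What remains is that section 7.3 says the study shall support the claim and offers only this figure and this measure for it.

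Second, the definition of the index may properly be left to the statistical analysis plan announced in section 11.8. If it is computed per patient, the descriptive statistics in section 11.1 would already give much of the per-patient distribution. That also stands, and the missing definition is not held against the protocol. Step 1 shows that the mismatch persists whether the 90% is pooled or applied patient by patient.

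Third, a reader might infer that the index is reached almost surely while most patients miss days. This is not general. At true rates of 90% to 91% the chance of exceeding 90% is only 49% to 89%. Most patients miss a day only below about 97.7% with independent days, and at a rate of 95% the share drops to half or fewer from a correlation of about 0.1. The protocol gives neither the rate nor the correlation. Since each patient has their own transmitter on a cellular network, clustering is at least as plausible as independence.

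Fourth, a reader might infer that a missed message is lost data or a safety problem. Section 4.1.1 says data are stored in the implant, and section 4.7.1.1 says daily R-wave and noise values are kept as trends. A missed message therefore means delayed availability, not necessarily loss. No patient-management decision in the protocol depends on the index, and adverse events are also collected at the 1-week visit and by telephone. Listing missing transmissions in section 18.7 is ordinary risk disclosure: it shows that gaps are foreseen, not how often they occur.

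**Conclusion.** The point holds as a mismatch between a stated claim and the measure offered for it. The conclusion rests on Step 1 alone: a level just above 90% permits just under 3 missing messages in 30 per patient on average, so reaching it supports a statement about average transmission success and no more.

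The model figures only illustrate the size. At an assumed true rate of 95% the index clears 90% with probability 0.98 or higher across the correlations tried, while between 23% and 79% of patients miss at least one day. They depend on the assumed rate, the 45 × 30 layout, the assumed definition of the index and the beta-binomial form of the clustering. No hypothesis test or participant protection is affected. The change is still worth making before results are read, because Table 1 fixes the claims in advance.

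**What to change.** In Table 1, replace the guarantee of daily availability with wording that matches the index, for example transmission success on more than 90% of days.

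In section 7.2.2, beside the overall index, add three summaries from data already in the HMSC:

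- the distribution of transmission success per patient;
- the proportion of patients with every expected day transmitted;
- the longest gap in days.

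Keep a daily-availability claim only if those per-patient results show it.

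The cost is one reworded table entry, one small extra table and a less favourable promotional statement. No visit, procedure or sample-size change is needed.

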Furthermore, ECG monitoring is crucial in assessing the efficacy of rhythm control therapies in patients with established AF. Since the distribution and duration of AF recurrences is often stochastic, ICMs play an important role in patients with infrequent symptoms and suspected arrhythmias. The capabilities of these devices open a wide field of diagnostic potential⁴. The experiences with the second generation of BIOTRONIK's ICM – BioMonitor 2 - since its market introduction in 2015 established the efficacy of its arrhythmia detection software. These well-established software algorithms have now been adopted in the smaller hardware of the BIOMONITOR III.

BIOMONITOR III - like its predecessor ICMs - is equipped with the Home Monitoring feature, which supports the daily transmission of device stored data including recordings of the subcutaneous ECG triggered by automatic detection, periodic recording or patient activation.

The third generational ICM, BIOMONITOR III, is the subject of this investigational study. The most important improvement over its predecessor is its miniaturization while retaining a particularly long sensing vector. This feature will provide large R-wave amplitudes and due to fractal coating of the electrodes improve P-wave visibility, yielding a higher diagnostic value. Miniaturization of the device will improve wearing comfort and allows for an easier, injection-like insertion procedure.

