4.7 Description of the investigational device

4.7.1 BIOMONITOR III

BIOMONITOR III represents BIOTRONIK's third generation of Implantable Cardiac Monitor (ICM) systems. BIOMONITOR III continually monitors the incoming cardiac signals and applies various automatic detection criteria, which are all based on R-R interval analysis.

Programmable parameters allow to patient-individually adjusting the implant for diagnosis, early detection or therapy monitoring. The device is not intended to deliver any therapy.

The implantable cardiac monitor BIOMONITOR III is premounted onto the FIT OneStep insertion tool. The assembly is provided in a single blister, together with an incision tool.

Via the optional Remote Assistant III, the recording of subcutaneous electrograms (sECG) can be triggered by the patient in case of symptomatic episodes.

It should be understood that the BIOMONITOR III does not make rhythm diagnosis. It is designed to detect suspicious rhythm segments and store their sECG to allow the physician to

decide if an arrhythmia was present. For example, a detection of 'high ventricular rate' can be normal sinus rhythm during exercise, a ventricular or supraventricular tachycardia or atrial fibrillation with rapid conduction. The device will record rhythm segments depending on the programming; 'true' arrhythmias (such that the physician wanted to detect) may remain undetected and 'false' detections (such that the physician did not want to detect) may be recorded. It is the task of the user to program the device according to the indication of the patient and the respective 'costs' of under- and over-detection.

4.7.1.1 sECG sensing and noise

The BIOMONITOR III features a combination of a rigid and a flexible part of the device body as shown in Figure below (Figure 2). The total device length is 78 mm. The overall device length defines the sensing vector of the ICM (i.e. electrode spacing) and correlates approximately linearly with the sensing amplitude. The rear end of the housing, as well as the lead tip, constitute the ICM's sensing electrodes and are fractally coated with iridium. The flexible part consists of a silicone lead body and a titanium cap and contains the electrode. The rigid part consists of titanium housing and is coated with silicone.

[figure not shown]

Figure 2: BIOMONITOR III shape and sensing vector

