8.2.1 Description of exposure to the investigational device and/or comparator

No comparator is used in this study.

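### Table 1 says the study shall support sensitivity, specificity and NPV claims for arrhythmia detection, but with no reference ECG and almost no record of undetected time, at most PPV could be estimated

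*Protocol*

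**What the plan says.** Protocol section 7.3 introduces Table 1 with "In this clinical investigation the following promotional claims shall be supported". Three rows concern detection performance:

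- Asystole: "State-of-the-art asystole detection (sensitivity, specificity, positive-predictive-value and negative-predictive-value) in combination with superior R-wave sensing"
- AF: "State-of-the-art AF-detection (sensitivity, specificity, positive-predictive-value and negative-predictive-value) in combination with superior R-wave sensing"
- Bradycardia, high ventricular rate and sudden rate drop: "State-of-the-art arrhythmia-detection (sensitivity, specificity, positive-predictive-value and negative-predictive-value) in combination with superior R-wave sensing"

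The same rows also call the diagnosis highly sensitive and highly specific. For all three, the related-data column has one entry, which begins "Supportive episode data collection (Home Monitoring".

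Elsewhere the protocol describes what those data contain:

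- Section 3 says Home Monitoring carries "recordings of the subcutaneous ECG triggered by automatic detection, periodic recording or patient activation".
- Table 2 and section 9.3.2 set the periodic sECG to once a day.
- Sections 9.4 and 9.5 have the investigator read three periodic strips per patient (two at 1 week, one at 1 month), counting P-waves in patients in sinus rhythm.
- Section 4.7.1 accepts that true "arrhythmias (such that the physician wanted to detect) may remain undetected".
- Table 2 lists no Holter, surface ECG or other independent rhythm record. On comparators, section 8.2.1 says "No comparator is used in this study".

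**The concern.** Sensitivity, specificity and NPV each depend on events or periods in which the device stayed silent. To count them, someone must know the true rhythm during that silence. The plan collects detected episodes, one short strip a day and recordings that the patient chooses to trigger, and it asks nobody to judge whether an arrhythmia was present or missed.

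What is at stake is how the results are used. Section 11.6 plans an interim analysis to inform the product-launch decision. The figure that detected episodes yield most naturally is a PPV; section 6.1 quotes one for another monitor, with 55 percent of AF detections confirmed. Under the wording of Table 1, a good PPV could be taken as evidence of sensitivity, while a missed asystole or AF episode would leave almost no trace in the data.

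**Working it through.** The protocol gives no detection-performance figure to reproduce, so the check asks which measures the planned data can identify.

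**1. What each measure needs** (TP, FP, FN, TN = true and false positives and negatives)

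- PPV = TP/(TP+FP)
- Sensitivity = TP/(TP+FN)
- Specificity = TN/(TN+FP)
- NPV = TN/(TN+FN)

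Detection-triggered episodes, once adjudicated, give TP and FP only. That fixes PPV; the other three need FN or TN.

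**2. Illustration** (assumed counts TP = 90, FP = 10). PPV is 90/100 = 0.90 whatever was missed.

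| Unseen misses (FN) | Sensitivity | PPV |
|---|---|---|
| 0 | 90/90 = 1.00 | 0.90 |
| 10 | 90/100 = 0.90 | 0.90 |
| 90 | 90/180 = 0.50 | 0.90 |
| 900 | 90/990 = 0.09 | 0.90 |

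The episodes alone cannot tell these rows apart.

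**3. How much undetected time the periodic strips capture.** Inputs are 45 patients (section 11.2), one strip per day (Table 2) and about 30 days of observation. The protocol does not state the periodic strip length. I assume 60 s, the length given for an AF recording in section 4.7.1.8, with a range of 30 to 120 s.

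- Strips: 45 × 30 = 1,350
- Recorded time: 1,350 × 60 s = 22.5 h, out of 45 × 30 × 24 = 32,400 h
- Fraction: 60/86,400 = 0.07% (30/86,400 = 0.03%; 120/86,400 = 0.14%)

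**4. Chance that a strip reveals a miss**

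- A missed 5 s asystole overlaps that day's strip with probability about (60+5)/86,400 = 0.0008 (0.0004 to 0.0014 over the range).
- For AF, at assumed burdens of 0.1%, 1% and 5%, the expected number of strips in AF is 1,350 × burden, or about 1, 14 and 68. These would cluster in a few patients.

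**5. What is actually read.** The planned reading is 3 × 45 = 135 strips, or 135/1,350 = 10% of those recorded. It covers P-waves in sinus rhythm, so a strip showing AF is not scored for detection.

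**6. Other sources.** Patient-triggered strips are selected by symptoms and are not a representative sample of undetected time. The 1-week RAM dump (section 9.7) reads the device's own memory and supplies no independent reference.

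**The case against.** The strongest reply is that the plan never sets out to estimate these measures. Sections 7.2.2 and 7.5 list no detection-performance variable, section 7.2 calls all analyses explorative, section 11.5 has no pass/fail criterion, and Table 1 labels the episode data as supportive. Section 4.1.1 already rests algorithm performance on clip testing and predecessor studies. All of this stands, and it confines the problem to Table 1: no endpoint, sample size or patient procedure depends on these rows. It does not remove the problem, because the table's lead-in says that this investigation shall support the claims, and the claims name the measures.

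A separate SAP could add adjudication of transmitted episodes. That would rescue PPV, but it cannot recover rhythm that was never recorded.

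A reader might infer three stronger points that the documents do not support:

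- **That Home Monitoring holds only what the device detected, so the data say nothing about misses.** Section 3 and Table 2 contradict this. Periodic and patient-triggered strips do sample undetected time, and a crude strip-level AF estimate is conceivable. It is thin, comes from the same device and is not planned; for brief events such as asystole it is of no practical use.
- **That the report will state a sensitivity figure.** The protocol plans none. The risk lies in how Table 1 may be read.
- **That 'superior' and 'industry-leading' R-wave sensing fails for the same reason.** R-wave amplitude is measured directly at insertion, 1 week and 1 month. What is missing is a concurrent comparator, a separate and lesser matter.

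**Conclusion.** The concern holds for sensitivity, specificity and NPV in the three detection rows of Table 1. As designed, the study has no reference rhythm, no planned arrhythmia reading of undetected time, and periodic coverage of about 0.07% of that time (0.03% to 0.14%). PPV is attainable only if transmitted episodes are adjudicated, which the protocol does not schedule.

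The coverage figure rests on the assumed strip length and about 30 days per patient. The counts in the sensitivity illustration are arbitrary and do not bound this trial's sensitivity. The conclusion itself needs neither; it follows from the absence of any reference for the time when the device did not fire.

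As a secondary point, the words 'superior' and 'industry-leading' for R-wave sensing have no concurrent comparator behind them. A historical comparison with BioMonitor 2 is possible, but it could not show leadership over competitors' devices.

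**What to change.** In the asystole, AF and bradycardia/high-rate/rate-drop rows of Table 1, delete sensitivity, specificity and NPV, and the 'highly sensitive' and 'highly specific' wording, as claims supported by this study. Refer them to the clip-test and predecessor-study evidence cited in section 4.1.1.

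Keep PPV only if the investigator's classification of each transmitted episode is recorded. Report it as the PPV of transmitted episodes, because section 4.1.1 says that storage and transmission are prioritised. Give it by detection type, among patients with at least one episode of that type (a per-patient value is undefined for the others), with an interval that accounts for clustering within patient.

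Separately, replace 'superior' and 'industry-leading' with descriptive R-wave results set beside the 1-week BioMonitor 2 means in section 5.2 (0.7 mV in the pilot study, 0.75 mV in the master study), labelled as a historical comparison.

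The cost is a wording change and narrower promotional claims, plus episode classification work if PPV is kept. PPV is not a mere tabulation of data already planned.
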